 b) Documents pertinent information assigned to the investigational device (e.g., date, quantity, batch or serial number, expiration date if applicable, and unique code number): *Write here*
 c) Stores the investigational device according to the manufacturer's recommendations with respect to temperature, humidity, lighting, and other environmental considerations: *Write here*
 d) Ensures that the device is stored in a secure area with limited access in accordance with applicable regulatory requirements: *Write here*
 e) Distributes the investigational device to subjects enrolled in the IRB-approved protocol: *Write here*

SECTION III: RECRUITMENT/CONSENT AND ASSENT PROCEDURES

1. **Targeted Enrollment:** Give the number of subjects:

a. Targeted for enrollment at Yale for this protocol: 60
 b. If this is a multi-site study, give the total number of subjects targeted across all sites: *Write here*

2. **Indicate recruitment methods below** . Attach copies of any recruitment materials that will be used.

 Flyers	 Internet/web postings	 Radio
 Posters	 Mass email solicitation	 Telephone
 Letter	 Departmental/Center website	 Television
 Medical record review*	 Departmental/Center research boards	 Newspaper

Departmental/Center newsletters Web-based clinical trial registries Clinicaltrials.gov
 YCCI Recruitment database Social Media (Twitter/Facebook):
 Other:

* Requests for medical records should be made through JDAT as described at
<http://medicine.yale.edu/ycci/oncore/availableservices/datarequests/datarequests.aspx>

3. Recruitment Procedures:

- Describe how potential subjects will be identified. We will use the YCCI subject database.
- Describe how potential subjects are contacted. We will use the YCCI subject database.

Who is recruiting potential subjects? *The investigators have employed the services of the Yale Center for Clinical Investigation/CTSA for recruitment for this study, including dedicated recruitment staff, community outreach personnel, as well as the use of the websites www.yalestudies.org and www.researchmatch.org with targeted recruitment information for both patients and healthcare professionals.*

The project manager will primarily oversee screening and recruitment.

4. Assessment of Current Health Provider Relationship for HIPAA Consideration:

Does the Investigator or any member of the research team have a direct existing clinical relationship with any potential subject?

Yes, all subjects
 Yes, some of the subjects
 No

If yes, describe the nature of this relationship. *Write here*

5. Request for waiver of HIPAA authorization: (When requesting a waiver of HIPAA Authorization for either the entire study, or for recruitment purposes only. Note: if you are collecting PHI as part of a phone or email screen, you must request a HIPAA waiver for recruitment purposes.)

Choose one:

For entire study
 For recruitment/screening purposes only
 For inclusion of non-English speaking subject if short form is being used and there is no translated HIPAA research authorization form available on the University's HIPAA website at hipaa.yale.edu.

i. Describe why it would be impracticable to obtain the subject's authorization for use/disclosure of this data: *We are requesting a waiver of signed HIPAA authorization in order to undertake telephone and online survey screening to determine potential eligibility of interested subjects. Without a request of signed HIPAA authorization for telephone and online survey recruitment only, we would not be able to telephone screen or provide an online screening survey to participants.*

ii. If requesting a waiver of **signed** authorization, describe why it would be impracticable to obtain the subject's signed authorization for use/disclosure of this data: *By signing this protocol application, the investigator assures that the protected health information for which a Waiver of Authorization has been requested will not be reused or disclosed to any person or entity other than those listed in this application, except as required by law, for authorized oversight of this research study, or as specifically approved for use in another study by an IRB.*

The investigator assures that the protected health information for which a Waiver of Authorization has been requested will not be reused or disclosed to any person or entity other than those listed in this application, except as required by law, for authorized oversight of this research study, or as specifically approved for use in another study by an IRB.

Researchers are reminded that unauthorized disclosures of PHI to individuals outside of the Yale HIPAA-Covered entity must be accounted for in the “accounting for disclosures log”, by subject name, purpose, date, recipients, and a description of information provided. Logs are to be forwarded to the Deputy HIPAA Privacy Officer.

6. Process of Consent/Accent: Describe the setting and conditions under which consent/assent will be obtained, including parental permission or surrogate permission and the steps taken to ensure subjects' independent decision-making.

Prior to signing the consent document, study staff will provide subjects with additional information about the study and review the consent forms and other study-related documentation. All subjects participating in the study will provide written consent. All subjects will be informed of the option of not participating, or of stopping at any time during the interview.

7. Evaluation of Subject(s) Capacity to Provide Informed Consent/Accent: Indicate how the personnel obtaining consent will assess the potential subject's ability and capacity to consent to the research being proposed.

The Principal Investigator and project manager/coordinator will determine the ability and capacity of individuals to give consent by questioning during the process of consent. Potential subjects will be asked, “Could you explain to me what we are going to ask you to do in this study? This will help me to be sure that you understand the research,” as well as, “What more would you like to know about this study?” All subjects will be informed of the option of not participating, or of stopping at any time during the study

8. Non-English Speaking Subjects: Explain provisions in place to ensure comprehension for research involving non-English speaking subjects. If enrollment of these subjects is anticipated, translated copies of all consent materials must be submitted for approval prior to use.

As needed, we will utilize bilingual translators for the informed consent process.

As a limited alternative to the above requirement, will you use the short form* for consenting process if you unexpectedly encounter a non-English speaking individual interested in study participation and the translation of the long form is not possible prior to intended enrollment? YES NO

Note* If more than 2 study participants are enrolled using a short form translated into the same language, then the full consent form should be translated into that language for use the next time a subject speaking that language is to be enrolled.

Several translated short form templates are available on the HRPP website (yale.edu/hrpp) and translated HIPAA Research Authorization Forms are available on the HIPAA website (hipaa.yale.edu). If the translation of the short form is not available on our website, then the translated short form needs to be submitted to the IRB office for approval via modification prior to enrolling the subject. *Please review the guidance and presentation on use of the short form available on the HRPP website.*

If using a short form without a translated HIPAA Research Authorization Form, please request a HIPAA waiver in the section above.

9. Consent Waiver: In certain circumstances, the HIC may grant a waiver of signed consent, or a full waiver of consent, depending on the study. If you will request either a waiver of consent, or a waiver of signed consent for this study, complete the appropriate section below.

Not Requesting any consent waivers

Requesting a waiver of signed consent:

Recruitment/Screening only (*if for recruitment, the questions in the box below will apply to recruitment activities only*)

Entire Study (Note that an information sheet may be required.)

For a waiver of signed consent, address the following:

- Would the signed consent form be the only record linking the subject and the research? YES NO
- Does a breach of confidentiality constitute the principal risk to subjects? YES NO

OR

- Does the research pose greater than minimal risk? YES NO
- Does the research include any activities that would require signed consent in a non-research context? YES NO

Requesting a waiver of consent:

Recruitment/Screening only (*if for recruitment, the questions in the box below will apply to recruitment activities only*)

Entire Study

For a full waiver of consent, please address all of the following:

- Does the research pose greater than minimal risk to subjects?
 - Yes *If you answered yes, stop. A waiver cannot be granted.*
 - No
- Will the waiver adversely affect subjects' rights and welfare? YES NO
- Why would the research be impracticable to conduct without the waiver? *Write here*
- Where appropriate, how will pertinent information be returned to, or shared with subjects at a later date? *Write here*

SECTION IV: PROTECTION OF RESEARCH SUBJECTS

Confidentiality & Security of Data:

1. What protected health information (medical information along with the HIPAA identifiers) about subjects will be collected and used for the research? *Name, date of birth, telephone number(s), mailing address, email address, gender, weight and height (to calculate BMI), medications, other diagnoses. Only the investigators will have access to PHI.*
2. How will the research data be collected, recorded and stored? *Paper forms will be kept in each study participant's record and will be stored in a locked file cabinet in PI office at [name], room*

[name]. Only the PI and study staff will have access to the participant's records. Forms will be coded with subject number; no personally identifiable information will be associated with these forms.

3. How will the digital data be stored? CD DVD Flash Drive Portable Hard Drive Secured Server Laptop Computer Desktop Computer Other
4. What methods and procedures will be used to safeguard the confidentiality and security of the identifiable study data and the storage media indicated above during and after the subject's participation in the study? *All documents and subject information will be strictly maintained according to HIC and HIPAA regulations to ensure confidentiality at all times. Access to subject information will be limited to a "need to know" basis and all data will be coded to maintain confidentiality. Only those investigators with appropriate Human Subjects training will have access to subject data. All electronic files are encrypted and password protected; paper files are kept in locked file cabinets. All data will be managed to assure strict confidentiality of subjects at all times. In addition, all portable devices will contain encryption software per University policy 5100.*

All portable devices must contain encryption software, per University Policy 5100. If there is a technical reason a device cannot be encrypted please submit an exception request to the Information Security, Policy and Compliance Office by clicking on url <http://its.yale.edu/egrc> or email [contact]

5. What will be done with the data when the research is completed? Are there plans to destroy the identifiable data? If yes, describe how, by whom and when identifiers will be destroyed. If no, describe how the data and/or identifiers will be secured. *Once the research is complete, the data will be analyzed by all members of the study staff and a statistician. Data will be kept for five years after the study ends. Data will then be de-identified using a "Safe Harbor" (45CFR164.514(b)(2)) approach consistent with the HIPAA Privacy rule. De-identified data will be certified by a statistician that there is a very small risk that use of the protected health information could lead to a subject being identified. The principal investigator ([name]) is responsible for the implementation of data de-identification.*
6. If appropriate, has a Certificate of Confidentiality been obtained?

This is NIH funded and is covered a COC..

SECTION V: POTENTIAL BENEFITS

Potential Benefits: Identify any benefits that may be reasonably expected to result from the research, either to the subject(s) or to society at large. (Payment of subjects is not considered a benefit in this context of the risk benefit assessment.)

There will be no direct benefits of the proposed research to the participating human subjects.

SECTION VI: RESEARCH ALTERNATIVES AND ECONOMIC CONSIDERATIONS

1. **Alternatives:** What other alternatives are available to the study subjects outside of the research? *Alternatives to participating in the study is not to participate.* **Payments for Participation (Economic Considerations):** Describe any payments that will be made to subjects, the amount and schedule of payments, and the conditions for receiving this compensation.

Subjects will be remunerated \$75 at each visit through ePay system set up by the CSRU.

2. **Costs for Participation (Economic Considerations):** Clearly describe the subject's costs associated with participation in the research, and the interventions or procedures of the study that will be provided at no cost to subjects.

Subjects will not incur any costs associated with participation in the research besides transportation costs. Subjects will be provided parking passes at each visit to cover parking if they drive to their visit and park in the ProPark lot surrounding the building.

You will be compensated in the amount of \$75 at each visit for 4 weeks. The total amount you will be given in four weeks will be \$300 (\$75x4) if you complete all the visits required by the study. You will be provided parking passes at each visit to cover parking if you park in the ProPark lot surrounding the building.

In Case of Injury: This section is required for any research involving more than minimal risk, and for minimal risk research that presents the potential for physical harm (e.g., research involving blood draws).
This research does not involve more than minimal risk.

- a. Will medical treatment be available if research-related injury occurs? *YNHH emergency room.*
- b. Where and from whom may treatment be obtained? *YNHH emergency room.*
- c. Are there any limits to the treatment being provided? *Treatment will be provided at the current standard of care.*
- d. Who will pay for this treatment? *This will vary from subject to subject. The clinical trial will not pay for the treatment.*
- e. How will the medical treatment be accessed by subjects? *Subject will walk into the YNHH emergency room. If this is not possible they will be transported there by ambulance.*

IMPORTANT REMINDERS

Will this study have a billable service? Yes No

A billable service is defined as any service rendered to a study subject that, if he/she was not on a study, would normally generate a bill from either Yale-New Haven Hospital or Yale Medical Group to the patient or the patient's insurer. The service may or may not be performed by the research staff on your study, but may be provided by professionals within either Yale-New Haven Hospital or Yale Medical Group (examples include x-rays, MRIs, CT scans, specimens sent to central labs, or specimens sent to pathology). Notes: 1. There is no distinction made whether the service is paid for by the subject or their insurance (Standard of Care) or by the study's funding mechanism (Research Sponsored). 2. This generally includes new services or orders placed in EPIC for research subjects.

If answered, "yes", this study will need to be set up in OnCore, Yale's clinical research management system, for Epic to appropriately route research related charges. Please contact [contact]

Are there any procedures involved in this protocol that will be performed at YNHH or one of its affiliated entities?
Yes No

If Yes, please answer questions a through c and note instructions below.

- a. Does your YNHH privilege delineation currently include the **specific procedure** that you will perform? Yes No
- b. Will you be using any new equipment or equipment that you have not used in the past for this procedure? Yes No
- c. Will a novel approach using existing equipment be applied? Yes No

If you answered "no" to question 4a, or "yes" to question 4b or c, please contact the YNHH Department of Physician Services ([name]) for prior approval before commencing with your research protocol.

IMPORTANT REMINDER ABOUT RESEARCH AT YNHH

Please note that if this protocol includes Yale-New Haven Hospital patients, including patients at the HRU, the Principal Investigator and any co-investigators who are physicians or mid-level practitioners (includes PAs, APRNs, psychologists and speech pathologists) who may have direct patient contact with patients on YNHH premises must have medical staff appointment and appropriate clinical privileges at YNHH. If you are uncertain whether the study personnel meet the criteria, please telephone the Physician Services Department at [contact]. **By submitting this protocol as a PI, you attest that you and any co-investigator who may have patient contact has a medical staff appointment and appropriate clinical privileges at YNHH.**

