F) Pregnancy: *The chance of a female subject to become pregnant on a 4-week study is very less, if in case this does happen they will be asked to stop the drug and withdraw from the study immediately. We do not intend to follow the pregnancy and birth outcome.*

Drug preparation: Digoxin is commercially available as a 0.05mg/ml elixir (Boehringer Ingelheim). The appropriate dosing of digoxin and control will be prepared with the help of the Yale Center for Clinical Investigation (YCCI) as detailed in the facilities and resources. Stopping criteria: Subjects will be removed from the study if any serum digoxin level is above 0.8ng/ml, or if there are any abnormalities in blood tests or ECGs. Data from these subjects will not be used in the analysis. Analysis, expected outcome and alternative approaches: It is expected that there will not be a significant difference in the neutrophil ROS and monocyte qPCR results in control group A between the four time points. It is expected that for group B and C, both neutrophil ROS and monocyte qPCR levels will be lower at time points 1, 2, 3 weeks as compared to time 0, and as compared to all time points of group A. It is not clear if in group D time points of week 1, 2, and 3 will be any different from time point 0. For the time points where significant differences are found we will perform additional luminex assay with the supernatant using the luminex five plex panel (GM-CSF, IL-1B, IL-6, IL-8, TNF- α). There will also be an analysis of the production of ROS and qPCR levels in relation to serum digoxin levels at the time that the analysis samples were obtained. The combinations of these analysis will establish that digoxin taken orally is effective in reducing inflammatory responses, and will also provide information on dose response for oral dosing as well as serum concentrations.

5. Genetic Testing N/A

A. Describe

- i. the types of future research to be conducted using the materials, specifying if immortalization of cell lines, whole exome or genome sequencing, genome wide association studies, or animal studies are planned *Write here*
- ii. the plan for the collection of material or the conditions under which material will be received *Write here*
- iii. the types of information about the donor/individual contributors that will be entered into a database *Write here*
- iv. the methods to uphold confidentiality *Write here*

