7. *Treatment with prednisolone or pentoxifyllin for more than 3 days prior to inclusion/start date*

8. Active alcohol abuse (>50 g/day for men and >40 g/day for women) in the last 3 months
9. AST > ALT and total bilirubin > 3 mg/dl in the past 3 months
10. Liver biopsy and/or clinical picture consistent with alcoholic hepatitis
11. Lack of signed informed consent.
12. Known hypersensitivity to digoxin or other forms of digitalis, ventricular fibrillation.
13. Any significant medical conditions, any electrolyte abnormalities, over the counter medications, natural products and prescription drugs.
14. Breastfeeding mothers.

9. How will **eligibility** be determined, and by whom? Write here

The eligibility will be determined by PI and his team according to their IRB protocol.

10. **Risks:** Describe the reasonably foreseeable risks, including risks to subject privacy, discomforts, or inconveniences associated with subjects participating in the research.

The following risks are associated with participating in the study:

- Adverse effects from digoxin and its toxicity. Symptoms of digoxin toxicity include: confusion, irregular pulse, loss of appetite, nausea, vomiting, diarrhea, fast heartbeat, vision changes (which could be unusual, but includes blind spots, blurred vision, changes in how colors look, and seeing spots), decreased consciousness, decreased urine output, difficulty breathing when lying down, excessive nighttime urination, and overall swelling
- Allergic reaction to digoxin (nausea, vomiting, diarrhea, loss of appetite, weakness, dizziness, headache, anxiety, depression, slow heart rate, enlarged or tender breasts in men, or skin rash).
- Risks and discomforts of phlebotomy: To obtain detailed biochemical liver function tests and blood samples for research, blood sampling will be required. Patients will have 4 venipunctures during the period of evaluation (28 days). Each venipuncture will remove ~18 ml of blood. However, no more than 6 ml/kg will be drawn from any one person during this 4-week period. Blood collection by venipuncture is associated with mild discomfort, and possible risk of localized bruising, phlebitis, or extravasation. The risk of infection or fainting is extremely small.

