- a. What is the investigator's assessment of the overall risk level for subjects participating in this study? *Risks are minimal.*
- b. If children are involved, what is the investigator's assessment of the overall risk level for the children participating in this study? *Write here*
- c. Include an appropriate Data and Safety Monitoring Plan. Examples of DSMPs are available here <http://your.yale.edu/policies-procedures/forms/420-fr-01-data-and-safety-monitoring-plans-templates> for
 - i. Minimal risk
 - ii. Greater than minimal

Greater Than Minimal Risk DSMP

1. Personnel responsible for the safety review and its frequency:

The principal investigator will be responsible for monitoring the data, assuring protocol compliance, and conducting the safety reviews at the specified frequency, which must be conducted at a minimum of every 6 months (including when reapproval of the protocol is sought). During the review process, the principal investigator (monitor) will evaluate whether the study should continue unchanged, require modification/amendment, or close to enrollment. Either the principal investigator, the IRB have the authority to stop or suspend the study or require modifications.

2. The risks associated with the current study are deemed greater than minimal for the following reasons: (choose those that apply)

1. We do not view the risks associated with the _____ as minimal risks.
2. We do not view the risks associated with the combined use of _____ and _____ as minimal risks.
3. Given the now established safety and validity of the current drug _____ in our prior work, we do not view the proposed studies as high risk.
4. Given our experience with the combined co-administration _____, we do not view the proposed studies as high risk.

Although we have assessed the proposed study as one of greater than minimal risk, the potential exists for anticipated and/or unanticipated adverse events, serious or otherwise, to occur since it is not possible to predict with certainty the absolute risk in any given individual or in advance of first-hand

experience with the proposed study methods. Therefore, we provide a plan for monitoring the data and safety of the proposed study as follows:

3. Attribution of Adverse Events:

Adverse events will be monitored for each subject participating in the study and attributed to the study procedures / design by the principal investigator (*[name]*) according to the following categories:

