- a.) Definite: Adverse event is clearly related to investigational procedures(s)/agent(s).
- b.) Probable: Adverse event is likely related to investigational procedures(s)/agent(s).
- c.) Possible: Adverse event may be related to investigational procedures(s)/agent(s).
- d.) Unlikely: Adverse event is likely not to be related to the investigational procedures(s)/agent(s).
- e.) Unrelated: Adverse event is clearly not related to investigational procedures(s)/agent(s).

4. Plan for Grading Adverse Events:

The following scale will be used in grading the severity of adverse events noted during the study:

1. Mild adverse event
2. Moderate adverse event
3. Severe

5. Plan for Determining Seriousness of Adverse Events:

Serious Adverse Events:

In addition to grading the adverse event, the PI will determine whether the adverse event meets the criteria for a Serious Adverse Event (SAE). An adverse event is considered serious if it results in any of the following outcomes:

1. Death;
2. A life-threatening experience in-patient hospitalization or prolongation of existing hospitalization;
3. A persistent or significant disability or incapacity;
4. A congenital anomaly or birth defect; OR
5. Any other adverse event that, based upon appropriate medical judgment, may jeopardize the subject's health and may require medical or surgical intervention to prevent one of the other outcomes listed in this definition.

An adverse event may be graded as severe but still not meet the criteria for a Serious Adverse Event. Similarly, an adverse event may be graded as moderate but still meet the criteria for an SAE. It is important for the PI to consider the grade of the event as well as its "seriousness" when determining whether reporting to the IRB is necessary.

6. Plan for reporting UPIRSOs (including Adverse Events) to the IRB

The principal investigator will report the following types of events to the IRB:

Any incident, experience or outcome that meets ALL 3 of the following criteria:

1. Is unexpected (in terms of nature, specificity, severity, or frequency) given (a) the research procedures described in the protocol-related documents, such as the IRB-approved protocol and informed consent document and (b) the characteristics of the subject population being studied; AND

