2. Is related or possibly related to participation in the research (*possibly related* means there is a reasonable possibility that the incident, experience, or outcome may have been caused by the procedures involved in the research); AND
3. Suggests that the research places subjects or others at greater risk of harm (including physical, psychological, economic, legal, or social harm) than was previously known or recognized.

Unanticipated Problems Involving Risks to Subjects or Others (UPIRSOs) may be medical or non-medical in nature, and include – but are not limited to – *serious, unexpected, and related adverse events* and *unanticipated adverse device effects*. **Please note** that adverse events are reportable to the IRB as UPIRSOs **only** if they meet all 3 criteria listed above.

These UPIRSOs/SAEs will be reported to the IRB in accordance with IRB Policy 710, using the appropriate forms found on the website. All related events involving risk but not meeting the *prompt* reporting requirements described in IRB Policy 710 should be reported to the IRB in summary form at the time of continuing review. If appropriate, such summary may be a simple brief statement that events have occurred at the expected frequency and level of severity as previously documented. In lieu of a summary of external events, a current DSMB report can be submitted for research studies that are subject to oversight by a DSMB (or other monitoring entity that is monitoring the study on behalf of an industry sponsor).

7. Plan for reporting adverse events to co-investigators on the study, as appropriate the protocol's research monitor(s), e.g., industrial sponsor, Yale Cancer Center Data and Safety Monitoring Committee (DSMC), Protocol Review Committee (PRC), DSMBs, study sponsors, funding and regulatory agencies, and regulatory and decision-making bodies.

For the current study, the following individuals, funding, and/or regulatory agencies will be notified (choose those that apply):

- All Co-Investigators listed on the protocol.
- Yale Cancer Center Data and Safety Monitoring Committee (DSMC)

X National Institutes of Health

- Food and Drug Administration (Physician-Sponsored IND #_____)
- Medical Research Foundation (Grant_____)

- Study Sponsor
- Other Data Safety Monitoring Board (DSMB) or Committee (DSMC)

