Adherence analysis will be ascertained using pill counts for each participant at the weekly visits. For safety analyses, we will record any adverse events, both serious (SAE) and not, described by the participant at each weekly visit. Each AE will include a description of the AE/SAE, relatedness to digoxin, and resolution. These will be summarized by treatment group and, if there are three or more participants in any one group with a specific AE/SAE, we will conduct a statistical test (Likelihood Ratio Chi-Square) to determine any statistically significant difference among the treatment groups using the analogous approach as above to first test for any difference in the incidence of AE/SAE among the three treatment groups followed by conducting the three pairwise comparisons, again using the Likelihood Ratio Chi-Square. Because this is a safety analysis, the critical p-value is left at 0.05 for all comparisons to avoid increasing the probability of a Type II error.

SECTION II: RESEARCH INVOLVING DRUGS, BIOLOGICS, RADIOTRACERS, PLACEBOS AND DEVICES

If this section (or one of its parts, A or B) is not applicable, check off N/A and delete the rest of the section.

A. RADIOTRACERS

N/A

1. Name of the radiotracer: *Write here*
2. Is the radiotracer FDA approved? YES NO

If NO, an FDA issued IND is required for the investigational use unless RDRC assumes oversight.

3. Check one: IND# *Write here* or RDRC oversight (RDRC approval will be required prior to use)
4. **Background Information:** Provide a description of previous human use, known risks, and data addressing dosage(s), interval(s), route(s) of administration, and any other factors that might influence risks. If this is the first time this radiotracer is being administered to humans, include relevant data on animal models.
Write here
4. **Source:** Identify the source of the radiotracer to be used. *Write here*
5. **Storage, Preparation and Use:** Describe the method of storage, preparation, stability information, method of sterilization and method of testing sterility and pyrogenicity.
Write here

B. DRUGS/BIOLOGICS

N/A

1. If an **exemption from IND filing requirements** is sought for a clinical investigation of a drug product that is lawfully marketed in the United States, review the following categories and complete the category that applies (and delete the inapplicable categories):

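### The plan openly declines to follow pregnancy and birth outcome, so a congenital anomaly after exposure to study drug would reach the principal investigator only by unsolicited report

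*Combined protocol and SAP*

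**What the plan says.** Section I, item 4 (Research Plan), part F deals with pregnancy during the study. It calls the chance very low in a 4-week study. If it happens, subjects are told that "they will be asked to stop the drug and withdraw from the study immediately", and then: "We do not intend to follow the pregnancy and birth outcome".

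Section I, item 12 (DSMP), part 5 has the PI judge whether each adverse event is serious against a list of outcomes. One entry reads "A congenital anomaly or birth defect; OR".

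Section I, item 13 (Statistical Considerations) describes safety data collection: "we will record any adverse events, both serious (SAE) and not, described by the participant at each weekly visit". On analysis it says "These will be summarized by treatment group". Section I, item 10 (Risks) gives a 28-day evaluation period.

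**The concern.** A birth outcome becomes known months after a 4-week study. The plan names one such outcome as serious, but withdraws the pregnant subject from the visits at which events are recorded and says it will not seek the result. If a subject takes study drug while pregnant, the outcome enters the safety record only if she, or someone for her, thinks to report it.

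What is at stake is limited but real. Subjects are healthy volunteers who gain no direct benefit (Section V). Without the outcome, the PI cannot apply to that pregnancy the attribution and seriousness steps already written into DSMP parts 3 and 5. The plan's only stated reason is low probability. That explains why follow-up would seldom be needed; it does not explain why a pregnancy that does occur should go unfollowed.

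**Working it through.** The plan gives no figure to reproduce. The check is whether any planned contact or review could reach a birth outcome.

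- **Weekly visits (item 13).** Events are recorded as the participant describes them. A pregnant subject leaves these visits at withdrawal. With samples at weeks 0, 1, 2 and 3, withdrawal at week w forgoes 3 − w visits: 2, 1 or 0 for w = 1, 2 or 3. Even a subject who completes is seen for at most about 28 days.
- **Tolerability contact (item 11, point 5).** One contact, within three days of starting drug. Far too early.
- **Pregnancy testing (items 4 and 11).** It can detect a pregnancy, not its outcome. No repeat schedule is clearly stated.
- **PI review as each subject completes (DMSP part 7, in item 12).** It reviews events already recorded and schedules no contact.
- **Periodic safety review (DSMP part 1),** "which must be conducted at a minimum of every 6 months". It may fall after a birth, but it too works from data in hand.
- **Reporting to the ethics board (DSMP part 6).** This governs events the PI already knows of. They must meet three criteria, one being "Is related or possibly related to participation in the research". It is a route for a report once received, not a way of obtaining one.

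Planned contacts that seek a birth outcome: 0.

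A timeline confirms that none does so by accident. The inputs are a last planned contact no later than week 4 (from the 28 days) and an assumed 35 to 40 weeks from conception to term birth, which is not in the documents.

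- Conception at first dose, last contact at week 4: 0 + 35 − 4 = 31 weeks from last contact to birth.
- Conception at the last contact, at week L: L + 40 − L = 40 weeks.
- Conception b weeks before first dose, missed at baseline: the shortest gap becomes 31 − b weeks. A term birth would fall inside planned contact only if b were about 31 weeks. That is not credible when pregnancy is an exclusion and is tested for.

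These week counts show only that birth lies outside the planned contacts. They do not measure harm. The documents give no basis for an expected number of pregnancies, and none is offered.

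**The case against.** The strongest reply is that this is a stated choice with a stated reason. Pregnancy is excluded at entry, testing is planned, dosing is short, and drug stops at once if pregnancy is found. The groups listed total 3 × 15 = 45 subjects (60 under Subject Population and Targeted Enrollment), so the event may never occur. All of this stands, and it keeps the severity low. It does not answer the point in full: part F itself provides for a pregnancy on study, and rarity also makes follow-up almost free.

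A second reply concerns the DSMP. A reader might infer that listing congenital anomaly as serious while declining to follow births makes the protocol contradict itself. The documents do not support that. The list defines when an event counts as serious; it does not promise to search for every listed outcome. Parts of the DSMP are also unfilled template text. Nor does the plan schedule post-study contact to look for a late death or disability.

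A reader might also infer that such an anomaly could never enter the record. That too goes too far: an unsolicited report could be classified under DSMP part 5 and, if it met all three criteria, reported under part 6.

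Privacy is a fair objection. Part B of the Research Plan aims to keep identifiable data to a minimum, and follow-up would add some about the pregnancy and infant.

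**Conclusion.** The point holds as a low-severity safety improvement. Under the current rule, an anomaly in a pregnancy exposed to study drug would be known only through passive reporting. The change takes planned outcome contacts from zero to one or two for each pregnancy the PI knows of. One followed pregnancy would support a judgement on that case; it would not estimate a drug effect.

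Nothing here shows that digoxin carries fetal risk, and the documents are not read as saying so. Nor should a reader infer damage to the efficacy analysis: the mixed models, sample size and alpha are unaffected.

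The conclusion rests on the text of the plan and on birth falling well after week 4. The consent pages are not in the public document. If they already ask subjects to report later pregnancies, that part of the fix is in place, but the stated rule against follow-up would still need to change.

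**What to change.** In Section I, item 4, part F, delete "We do not intend to follow the pregnancy and birth outcome" and put in its place:

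*Any pregnancy in which the subject took at least one dose of study drug (any group), whether conceived before or after first dose, that is detected by study testing or reported by the subject, is reported to the PI; with her consent, the outcome is obtained by telephone and assessed against the SAE list in the DSMP.*

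Keep the stop-drug and withdrawal rule. At the last visit, ask subjects to report a pregnancy recognised later that may have been exposed; a conception late in the study may not be apparent by then.

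Covering conception before first dose matters because a pregnancy missed at baseline and found on study is also exposed. Covering every group keeps ascertainment equal across the groups by which adverse events are summarised. To limit personal health information, record only the pregnancy outcome and any congenital anomaly, on a form coded by subject number as in Section IV, item 2.

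The cost is an ethics-reviewed change to protocol and consent wording, one question at an existing visit, and one or two calls per pregnancy. Telephone numbers are already collected (Section IV, item 1). No visits, tests or subjects are added. The downsides are rare contact with a withdrawn subject, who may decline, and a small amount of added personal health information. A pregnancy recognised after the last visit would still depend on the subject reporting it, though she would now have been asked to.
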